### 3.9.3 Outcomes at a service level

For the aggregate outcomes for each service, we will use summarised data only.

#### LLBD Weight Management Programme sample size calculation

From January to March 2023 the mean starting weight was 103.68kg. The mean weight on completion of the 12 week course was 99.60kg. So, the mean weight loss was 4.08 kg for this cohort. This was larger than the mean weight loss of 2.3 kg for behavioural weight management interventions in primary care at 12 months compared with controls (Madigan *et al*, 2022). But people can gain weight after initial loss so we are happy to use the historical Derbyshire data to help calculate a required sample size.

We expect the mean weight loss for the Derbyshire service to be larger in 2024 than in early 2023 potentially due to the health literacy training but also likely to be related to improvements management have made to the service between 2023 and 2024.

We would expect a minimum of a 10% increase in the mean weight loss in the trained group vs. untrained group at 12 weeks, that is, 4.7kg vs. 4.3kg. With an estimated pooled standard deviation of 1.6, a sample size of 252 would be required in each group to detect this size of difference with 80% power at a 5% level of significance. As stated earlier there will be approximately 330 service users in each group who can be invited to take part. We therefore should be able to recruit sufficient numbers (252) to ensure we will be able to detect an improvement in weight loss over time at a service level.

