### LLBD weight management programme

- Mean weight and standard deviation at baseline, 12 weeks and 26 weeks
- Mean weight loss and standard deviation between baseline and 12 weeks, and between baseline and 26 weeks.
- Mean score on the short form Warwick and Edinburgh Mental Health and Wellbeing Scale and standard deviation at baseline and 12 weeks.
- Mean change in the short form Warwick and Edinburgh Mental Health and Wellbeing Scale and standard deviation between baseline and 12 weeks s.

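### The 252-per-group figure rests on a 1.6 kg standard deviation whose source is not stated, so the 80% power is unverified and highly sensitive to it

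*Combined protocol and SAP*

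**What the plan says.** The calculation is in section 3.9.3, under the LLBD Weight Management Programme sample size heading.

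- **Means.** These come from an identified cohort: "From January to March 2023 the mean starting weight was 103.68kg", with 99.60 kg on completing the course. "So, the mean weight loss was 4.08 kg for this cohort". The team adds that "we are happy to use the historical Derbyshire data to help calculate a required sample size".
- **Effect.** The target is a "10% increase in the mean weight loss in the trained group vs. untrained group at 12 weeks, that is, 4.7kg vs. 4.3kg".
- **Spread.** "With an estimated pooled standard deviation of 1.6" is all that is said. No unit, cohort, citation, derivation or sensitivity range follows, and no other section gives an SD for weight or weight loss.
- **Result.** "a sample size of 252 would be required in each group", "with 80% power at a 5% level of significance". The paragraph notes about 330 people per group who can be invited, and concludes that the numbers are enough to be sure of detecting an improvement at service level.

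Two other places bear on this. Section 3.9.2 expects a 50% response, giving about 160 individual-level participants per group. Section 3.7 asks the service for "Mean weight loss and standard deviation between baseline and 12 weeks, and between baseline and 26 weeks", covering a 2024 delivery period and the corresponding period in 2023.

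**The concern.** Required sample size rises with the square of the SD, so the least documented input has great leverage on the result. The mean can be traced to a named cohort and the SD cannot, although the same records should yield both.

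The value also looks narrow against the plan's own means. Participants average about 104 kg at the start, and SD 1.6 kg with a roughly normal distribution would have practically everyone losing weight.

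What is at stake is interpretation. Weight is this service's primary outcome (section 3.5). Section 8 says that, if outcomes do not change, dissemination will concentrate on why they did not improve, to help commissioners decide on funding. If the real power is well under 80%, a null result could be read as failure of the training when the comparison was simply imprecise.

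**Working it through.** **Inputs.** From section 3.9.3: difference 4.7 − 4.3 = 0.4 kg; SD 1.6, taken as kg; 5% significance; 80% power; equal groups. Sidedness is not stated, but two-sided reproduces the figure and one-sided gives 198. From section 3.9.2: about 160 per group. SDs above 1.6 are assumptions, because the documents supply none.

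**Step 1: the plan's own figure.** n per group = 2 × (1.960 + 0.842)² × SD² / 0.4². With (1.960 + 0.842)² = 7.849 and SD 1.6, n = 2 × 7.849 × 2.56 / 0.16 = 251.2, rounded up to 252. The t-test version gives 252.1. The plan's figure is reproduced.

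**Step 2: what SD 1.6 implies.** Assuming normality, the share with no loss or a gain is Φ(−mean/SD).

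- Mean 4.08 kg: Φ(−2.55) = 0.54%
- Mean 4.3 kg: Φ(−2.69) = 0.36%
- Mean 4.7 kg: Φ(−2.94) = 0.17%

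The central 95% at mean 4.3 kg is 4.3 ± 1.96 × 1.6, or 1.2 to 7.4 kg lost.

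**Step 3: sensitivity to SD.** Power = Φ(0.4 / (SD × √(2/n)) − 1.96). The difference detectable at 80% power is 2.802 × SD × √(2/n). Example: SD 1.6 and n = 160 give a standard error of 1.6 × √(2/160) = 0.179. Power is then Φ(2.236 − 1.96) = 61%, and the detectable difference is 2.802 × 0.179 = 0.50 kg.

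| SD (kg) | n per group for 80% power | Power, 160 per group | Power, 252 per group | Power, 330 per group | Detectable, 160 (kg) | Detectable, 252 (kg) |
|---|---|---|---|---|---|---|
| 1.6 (plan) | 252 | 61% | 80% | 89% | 0.50 | 0.40 |
| 2 (assumed) | 393 | 43% | 61% | 73% | 0.63 | 0.50 |
| 2.5 (assumed) | 614 | 30% | 43% | 54% | 0.78 | 0.62 |
| 3 (assumed) | 883 | 22% | 32% | 40% | 0.94 | 0.75 |
| 4 (assumed) | 1,570 | 14% | 20% | 25% | 1.25 | 1.00 |

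These use the normal approximation; the t-test adds about one person per group. All ignore clustering by adviser and dropout.

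**Step 4: the largest SD the available numbers could bear.** If all 330 or so people per group contributed, 80% power for 0.4 kg would need SD no larger than 0.4 / (2.802 × √(2/330)) = 1.83 kg.

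**The case against.** The strongest reply is that nothing in the documents contradicts 1.6. It appears just after the statement that historical Derbyshire data will be used, and may well come from them. The 2023 mean is taken at completion of the course; if it describes completers, fewer people without weight loss would be expected than among all starters. The 0.4% also depends on normality. Without any shape assumption, the one-sided Chebyshev (Cantelli) bound on the share not losing weight is 2.56 / (2.56 + 4.3²) = 2.56 / 21.05 = 12%. That is an extreme bound, not a likely value, but it shows that mean and SD alone do not settle the matter.

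This stands against two tempting readings. A reader might infer that 252 is miscalculated; it is not. A reader might also infer that the true SD must be much larger and the power far below 80%. That needs a belief about how many attendees fail to lose weight, and no section gives that figure.

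The reply does not remove the missing source or the sensitivity. Nor can the regression in section 3.10.4 be assumed to close the gap. If the raw SD were 2.5, covariates would have to explain 1 − (1.6/2.5)² = 59% of the variance in loss to bring it down to 1.6, and the calculation claims no such gain.

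It can fairly be said that section 3.9.3 concerns aggregate data, which do not depend on individual consent, so about 330 per group might contribute. At SD 1.6 that gives 89% power. But the paragraph itself argues in terms of inviting and recruiting 252, so the number that applies needs stating.

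Finally, everyone who starts is invited, so the SD does not set enrolment. That limits the consequence to what the plan claims and how a result is read.

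**Conclusion.** The point holds as an unsupported sample-size assumption, not an arithmetic error. The 252 is right for its inputs, but the source of the SD is not stated and the value looks narrow under normality.

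The stated 80% power is therefore unverified and highly sensitive. An SD of 2 kg would cut it to 61% at 252 per group, and 3 kg to 32%. These SDs are illustrations; if the 2023 cohort showed an SD near 1.6, the 80% at 252 per group would stand, clustering apart.

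One shortfall needs no assumed SD. The plan's own expectation of about 160 individual-level participants per group gives about 61% power at SD 1.6. The assurance of detection is too strong on either count. It is also worded as improvement over time, whereas the calculation is for trained versus untrained groups. This is a worthwhile correction, held with medium confidence.

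**What to change.** 1. Ask the service for the SD of individual 12-week weight loss in the January–March 2023 cohort that supplied the 4.08 kg mean, and say whether it covers completers or all starters. This is a short additional request. The section 3.7 request is tied to the 2024 delivery period; section 6 puts training in July–August 2024 and service-user recruitment in July–November, so the matching 2023 window is probably not January–March.
2. Use that SD, with its unit and source, in section 3.9.3, and state that the test is two-sided.
3. Restate either the power for 0.4 kg or the difference detectable at 80% power for the numbers actually expected, separately for the individual-level and aggregate comparisons. At SD 1.6 the detectable difference is about 0.50 kg with 160 per group. Give a range over SD, as in the table, and say that clustering by adviser is ignored if it is.
4. Remove the assurance that the numbers will secure detection.

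The cost is one data request, a revised paragraph and probably a less favourable stated power. No extra enrolment is asked for.

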### **3.7. Assessment of changes in outcomes (at a service level)**

Aggregate programme level data will be obtained from the two services for a three - six month period in 2024 when trained staff have delivered programmes and a corresponding three- six month period in 2023. This will allow comparable measurement of change over time at a service level.

For the weight management service, a control group will consist of programmes run by non-trained staff. The same aggregated data will be obtained for this control group. Individual level patient data will not be shared with researchers because not all service users will have consented to this.

The aggregate data will include:

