### **3.8 Recruitment**

We will recruit staff delivering Verbal Health Literacy training during a three month period in 2024.

IRAS 336469

V2.0 13052024

We will recruit service users from two services, one within Derbyshire Community Health Services NHS Trust and one within the Local Authority. Service user recruitment is likely to take place over a six month period to recruit the minimum required sample. This is because both services run on a rolling basis. That is week 1 for one person could be week 6 for another.

We will recruit service users who enrol on the 12 week weight management programme and 6 week pulmonary rehabilitation programme after staff have (or have not) attended the Verbal Health Literacy training.

That is:

- Public Health Intervention Advisors and service users from the Live Life Better Derbyshire tier two weight management service.
- Physiotherapists, specialist nurses and service users from the Derbyshire Community Health Services (DCHS) pulmonary rehabilitation service.

Recruitment will commence once HRA and NHS ethics approval is obtained. Written informed consent will be gained for all participants in the study.

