### 3.9.2. Service users' individual outcomes

#### LLBD Weight Management Programme

Between 15-25 people attend each 12 week rolling LLBD weight management programme. 33 programmes are likely to be ongoing between the three month study period in 2024, with a minimum and maximum of 495 and 825 service users joining in total. All service users starting the programmes during the period of the study will be invited to take part when they sign up. We estimate there will be approximately 660 attendees to the LLBD weight management programme. With a response rate of 50% to our request to participate in the evaluation, we expect there to be weight, health and wellbeing and Health Literacy scores at three time points for approximately 330 service users. Approximately 160 service users will be in groups led by trained and 160 in groups led by untrained staff. We expect to see a reduction in weight, an improvement in clinical outcomes and an improvement in wellbeing between baseline and 12 weeks and baseline and 26 weeks for both groups. We expect the changes to be larger in the trained group versus the untrained group. We expect there to be an improvement in Health Literacy domain scores between baseline and 12 weeks (the end of the program) for the trained group and no change for the untrained group.

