#### 3.10.5 Aggregate service data

For the aggregated outcome data we will compare mean change in an outcome in a three month period before the training and in the three month period after the training for trained and untrained groups. Means and standard deviations will be provided by the services, that is, no individual data will be shared with researchers.

To meet the final objective, we will compare the IMD quintiles for attendees at the programmes in the three month period post-training with the IMD quintiles for the IRAS 336469

Derbyshire population. The expectation is that the % of people in socially deprived quintiles will be higher for the programmes than for the Derbyshire population.

SPSS and Excel spreadsheets will be used to store, organise and assist in analysis of the quantitative data from multiple sources.

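### Section 3.9.3 says 252 per group can be recruited from about 330 invited but applies no response rate; 252 is reachable in three months only as a count in the aggregate data, and the consented comparison has about 61% power

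*Combined protocol and SAP*

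**What the plan says.** Section 3.9.3 calculates 252 per group to detect 4.7 kg against 4.3 kg mean weight loss at 12 weeks, trained against untrained staff, with SD 1.6, 80% power and 5% significance. It continues: "As stated earlier there will be approximately 330 service users in each group who can be invited to take part". It then concludes: "We therefore should be able to recruit sufficient numbers (252) to ensure we will be able to detect an improvement in weight loss over time". The last words of that sentence, which follow the quoted part, place the claim at service level. Section 3.9.3 also opens with: "For the aggregate outcomes for each service, we will use summarised data only".

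Section 3.9.2 takes the same programme over three months, with 495 to 825 joiners and a working figure of 660. It makes an allowance that 3.9.3 does not: "With a response rate of 50% to our request to participate in the evaluation". The result is: "Approximately 160 service users will be in groups led by trained and 160 in groups led by untrained staff".

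The windows differ between sections:
- Section 3.8: "Service user recruitment is likely to take place over a six month period to recruit the minimum required sample".
- Section 6: service users are recruited from July to November 2024.
- Section 3.7: "Aggregate programme level data will be obtained from the two services for a three - six month period in 2024".
- Section 3.10.5: "we will compare mean change in an outcome in a three month period before the training and in the three month period after the training".

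**The concern.** The feasibility step treats the number who can be asked as if it were the number who will agree. One section earlier, half of the same intake is expected to agree. If 252 is a recruitment target, the protocol's own three-month figures miss it by about 90 per group.

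The cross-reference in 3.9.3 adds to the confusion. The 330 that appears in 3.9.2 is the expected number of responders in both groups together. The 330 per group in 3.9.3 is half of 660 attendees, before any response rate. The same number stands for two different quantities.

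Weight is the programme's primary outcome, and 252 is the only sample-size calculation for it. The individual-level test, the trained-against-untrained regression in section 3.10.4, has no power statement of its own. If it returned a null result, readers could give that result more weight than about 160 per group can bear.

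**Working it through.** **Inputs.** Difference 0.4 kg (4.7 − 4.3) and SD 1.6 from 3.9.3; 660 attendees (range 495 to 825) and 50% response from 3.9.2; about equal groups, since section 3.2 trains four of eight staff. The protocol does not state sidedness. A two-sided test reproduces its figure, whereas a one-sided test would give 198.

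**1. The plan's own figure.** n per group = 2 × (1.960 + 0.8416)² × (1.6/0.4)² = 251.2, rounded up to 252. It reproduces.

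**2. Response needed.** 252/330 = 0.764, or 76%, against the 50% assumed in 3.9.2.

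**3. Consented sample, three months.** Per group = attendees × 0.5 / 2. Power = Φ(0.25 × √(n/2) − 1.960), where 0.25 = 0.4/1.6.

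| Attendees | Consenting per group | Power for 0.4 kg |
|---|---|---|
| 495 | 124 | 50% |
| 660 | 165 (protocol rounds to 160) | 62% (61% at 160) |
| 825 | 206 | 72% |

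The target of 252 is not reached anywhere in the stated range. With 160 per group, the difference detectable with 80% power is 2.8016 × 1.6 × √(2/160) = 0.50 kg.

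**4. Aggregate data, three months, no consent needed.** Per group = attendees / 2.

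| Attendees | Per group | Power for 0.4 kg |
|---|---|---|
| 495 | 247.5 | 79% |
| 660 | 330 | 89% |

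These figures assume that every attendee has a 12-week weight. At 660 attendees, at least 76% (252/330) must have one. The documents give no completion rate.

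**5. Longer consented window.** At 165 per three months, each group gains 55 consenting users a month, so 252 takes 252/55 = 4.6 months. Six months gives 55 × 6 = 330 per group. Both figures assume that intake scales with time.

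**6. Clustering, as an assumption only.** The documents give no intracluster correlation (ICC). With four staff per group and 330 users per group, clusters average 82.5, and the design effect is 1 + 81.5 × ICC. An assumed ICC of 0.01 gives 1.815, an effective n of about 182 and 66% power. An assumed ICC of 0.05 gives 5.075, an effective n of about 65 and 30% power. The 89% is therefore a ceiling.

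**The case against.** The strongest reply is that 3.9.3 concerns service-level outcomes. Its heading says so, it opens by restricting itself to summary data, and the disputed sentence ends at service level. Section 3.7 explains that individual data are withheld because not everyone will have consented. A response rate to a research invitation has no place in such a count, and 330 exceeds 252. Section 3.9.2, which covers the consented sample, claims no power at all. In addition, section 3.8 foresees six months of recruitment.

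Much of this stands. A reader might infer that the protocol gives no basis for 252, that the service-level comparison cannot reach it, or that 80% power is claimed for both analyses. The documents support none of these. The summary-data basis is stated, about 330 per group are available on it in three months, and the individual-level section makes no power claim.

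The reply does not rescue the wording. Aggregate data involve no invitation and no recruitment, yet those are the terms of the argument. Section 3.8 also ties recruitment to a minimum required sample, and 252 per group is the only required service-user sample size in the protocol. The six months in 3.8 would help the consented sample, but 3.9.2 works with three months and section 6 with July to November. Finally, the calculation contrasts trained with untrained staff at 12 weeks, whereas the conclusion speaks of change over time.

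**Conclusion.** The calculation of 252 is correct, but the step from 330 invited to 252 recruited is not. On the protocol's own three-month figures the consented sample is about 160 per group, with 61% power for 0.4 kg (50% to 72% over the attendee range). Read as a count of service users in the aggregate data, 252 is reachable: about 330 per group and up to 89% power, or about 248 and 79% at the minimum intake.

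It would go too far to conclude that the weight comparison is infeasible. The defect is that 3.9.3 argues for a service-level comparison in the language of consent, while the individual-level regression is left without a power statement. It should be fixed.

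The figures rest on SD 1.6, a two-sided 5% test and equal groups. All are upper limits, before missing weights and before clustering within eight staff (four against four).

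**What to change.** In 3.9.3, replace the last two sentences of the weight-management calculation with two statements.

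- **Service level.** Say that 252 per group means service users with a 12-week weight in the aggregate data, for whom individual consent is not needed. Give one data window, reconciled between sections 3.7 and 3.10.5. Name the contrast as trained against untrained at 12 weeks. Remove the reference to change over time, or power that contrast separately.
- **Individual level (regression in 3.10.4).** Say that at 50% response about 160 per group are expected in three months, with about 61% power for 0.4 kg. If the six-month window in 3.8 is adopted instead, say about 330 per group, provided intake scales with time. Reconcile the windows in 3.8, 3.9.2 and section 6. Use the same period for both groups, as section 3.2 requires.

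Add that every power quoted is an upper limit, before missing weights and before clustering within the eight staff, for which no ICC is available. Unadjusted values should not be presented as achieved power.

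The cost is protocol wording. No extra participants are needed if the service-level reading is intended. The downside is a less favourable stated power for the individual-level comparison.

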## DCHS NHS Pulmonary Rehabilitation Programme

We would expect the increase in the mean CRDQ score at 6 weeks in 2024 (post training) to be larger than the increase in the mean CRDQ score in 2023 (pre training). We are unlikely to have statistical power to detect small differences based on numbers of service users if we limit the 'post' time period to the three month study period in 2024 and the corresponding 'pre' time period in 2023. We need to extend this request for data to cover a six month period.

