#### **3.2 Timing of intervention**

For both programmes staff will receive Verbal Health Literacy training and implementation support from the Health Literacy Officer. Outcomes will be measured for service users joining a programme run by trained staff. Where appropriate and for comparison, outcomes will be measured for service users joining a programme run by non-trained staff during the same period.

Half of the staff from the weight management programme (4/8) will receive the training to allow for controlled before and after comparison of outcomes. One member of staff takes a group of service users through their weight management sessions so it will be possible to identify service users linked to trained and untrained staff. This is not possible for the pulmonary rehabilitation service where different staff work with different service users throughout the programme. All six physiotherapists and two specialist nurses from the pulmonary rehabilitation service will receive the training. The focus is on physiotherapists and specialist nurses because they spend most time with service users.

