#### Primary outcomes

- LLBD Weight Management Programme: Weight in kilograms
- Pulmonary Rehabilitation Programme: The Chronic Respiratory Disease Questionnaire (CRDQ).

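### In pulmonary rehabilitation the only contrast bearing on a training effect is one 2024 period against the matching 2023 period, which cannot separate training from other change over the year

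*Combined protocol and SAP*

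**What the plan says.** All references are to the combined protocol and SAP.

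- **Outcome.** The list of primary outcomes in section 3.5 names, for this service, "Pulmonary Rehabilitation Programme: The Chronic Respiratory Disease Questionnaire (CRDQ"). It is measured at 0 and 6 weeks.
- **No untrained group.** Section 3.2 sets up a trained-untrained split in weight management, then says: "This is not possible for the pulmonary rehabilitation service where different staff work with different service users throughout the programme". It continues: "All six physiotherapists and two specialist nurses from the pulmonary rehabilitation service will receive the training".
- **Service-level comparison.** Section 3.7 compares a period in 2024 with "a corresponding three- six month period in 2023". The control there is for one service only: "For the weight management service, a control group will consist of programmes run by non-trained staff".
- **Hypothesis.** Section 3.9.3 (pulmonary rehabilitation) states: "We would expect the increase in the mean CRDQ score at 6 weeks in 2024 (post training) to be larger" than the 2023 increase. It gives no effect size or SD, doubts the power of a three-month window, and asks for six months of data.
- **Analysis.** Section 3.10.5 compares mean change in a three-month period before training with three months after, for trained and untrained groups. It describes no adjustment for trend or case mix.
- **Change expected in the other service.** Section 3.9.3 (weight management) says that a better 2024 result is potentially due to training but also "likely to be related to improvements management have made to the service between 2023 and 2024".

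**The concern.** Matching the calendar months deals with season. Nothing in the plan deals with what else may have changed in pulmonary rehabilitation between the two periods, such as staffing, referral pattern, case mix or programme content. The weight service has untrained advisers whose 2023-2024 change can be subtracted. Pulmonary rehabilitation has no such group, and no earlier or intermediate periods are requested in their place.

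CRDQ is a primary outcome, and objective (e) asks for the impact of training on health outcomes. Section 8 intends the results to inform commissioners' funding decisions. A higher CRDQ gain in 2024 could have been present before anyone was trained, and the data requested could not show whether it was.

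**Working it through.** **1. What each planned analysis can identify for this service**

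| Analysis | Where | Can it isolate a training effect on patient outcomes? |
|---|---|---|
| Change in CRDQ from 0 to 6 weeks, consented service users | 3.10.4 | No. All enrol after training (3.8), and 3.9.2 expects improvement from attending the programme. |
| Health Literacy Questionnaire improvement against CRDQ | 3.10.4 | No. It is an association within an exposed cohort. |
| Observations, staff questionnaires, focus groups | 3.3, 3.4, 3.10.1 to 3.10.3 | No. They concern staff behaviour and views. |
| 2024 gain against 2023 gain, aggregate | 3.7, 3.9.3, 3.10.5 | Only if nothing else changed between the periods. |

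The last row is the only one with an untrained comparator.

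**2. What extending to six months does**

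The plan has no sample size figure for this service to reproduce. Section 3.9.2 gives 96 to 144 attendees in three months (6 venues × 8 to 12 people × 2 cohorts). Doubling gives 192 to 288 in six months.

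Assumptions, none of them from the documents: equal numbers in each period, all attendees measured, a two-sided 5% normal test, zero training effect, and a non-training shift of d SDs of the CRDQ change, with d from 0.10 to 0.25.

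P(significant) = 1 − Φ(1.96 − d√(n/2)) + Φ(−1.96 − d√(n/2))

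For n = 96 and d = 0.10, d√(n/2) = 0.10 × √48 = 0.69, which gives 0.107.

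| n per period | d = 0 | d = 0.10 | d = 0.25 |
|---|---|---|---|
| 96 (3 months) | 5% | 11% | 41% |
| 144 (3 months) | 5% | 14% | 56% |
| 192 (6 months) | 5% | 17% | 69% |
| 288 (6 months) | 5% | 22% | 85% |

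If there is drift, a longer window makes a false attribution more likely, because the standard error shrinks and the bias does not.

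**3. Precision cost of a drift check**

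Assume 120 attendees per quarter (midpoint of 96 and 144), so 240 per half-year. The multiplier for 80% power is 1.96 + 0.84 = 2.80.

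- Two six-month blocks: 2.80 × √(2/240) = 0.26 SD detectable.
- The same, minus the January-June change between years: 2.80 × √(4/240) = 0.36 SD.
- Using October-December only, with July-September set aside as transitional: 2.80 × √(2/120 + 2/240) = 0.44 SD.
- The drift check alone has a 95% interval of about ±1.96 × √(2/240) = ±0.18 SD.

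**4. The weight-service calculation**

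2 × (1.96 + 0.84)² × 1.6² / 0.4² = 251.2, or 252 per group, which reproduces the stated figure. It sizes trained against untrained (4.7 v 4.3 kg). The sentence that follows concludes that the study can "detect an improvement in weight loss over time at a service level", which is a different contrast.

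**The case against.** The plan is open about the missing control. Section 3.1 promises controlled measurement only where possible, and section 3.2 explains why pulmonary rehabilitation cannot have it. Section 3.7 also requests summarised demographics, so a gross shift in case mix would be visible. This stands, but explaining why there is no control does not supply a substitute, and describing case mix does not adjust for it.

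Four stronger readings are tempting, and the documents do not support them.

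- **That all year-to-year change will be credited to training.** No section says so. Section 3.9.3 states an expectation and labels the periods as before and after training. The supportable statement is that the design cannot separate the two, and that no caution is written for this service.
- **That about a third of any CRDQ effect would be drift.** The weight figures give (4.3 − 4.08)/(4.7 − 4.08) = 0.22/0.62 = 35%. But 4.3 and 4.7 kg are planning values, and 4.08 kg is from January-March 2023, whereas section 6 recruits in July-November 2024. They concern another outcome in a service run by another organisation, so the proportion does not carry over.
- **That the Health Literacy Officer's earlier work on written materials shows drift here.** Section 1.3.3 counts 19 services but does not say that pulmonary rehabilitation was one of them, or that the work fell between the two periods.
- **That weight management has the same defect.** Sections 3.2, 3.7 and 3.10.5 already plan a controlled before-after comparison there. The phrase in section 3.9.3 is a wording slip.

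It is also fair to object that quarterly means are noisy and that a drift check cannot remove an abrupt change coinciding with training. Both stand, and they limit what the fix can claim.

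**Conclusion.** The concern holds for pulmonary rehabilitation. The 2024 v 2023 contrast is the only one bearing on a training effect, and it cannot separate training from other change in the service or its case mix. Extending it to six months adds precision without reducing that bias.

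The size of the bias is unknown: the documents give no CRDQ SD or effect, and they record no actual 2023-2024 change in this service. The 11-85% range in the table rests wholly on the assumed drift of 0.10 to 0.25 SD with no training effect. It shows how the bias behaves and is not a forecast. The relevance of drift rests on the authors' own expectation of non-training change over the same interval in the other service.

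**What to change.** 1. In section 3.7, request the pulmonary rehabilitation aggregates (n, mean change and SD of change for CRDQ and the secondary measures) by quarter of programme start, from January 2023 to the last post-training quarter. Section 6 puts training in July-August 2024, so January-June 2024 is pre-training. Mark July-September 2024 as transitional.
2. Keep the same-months 2023 v 2024 contrast. Report beside it the January-June 2024 minus January-June 2023 change, with its interval, as a check on drift before training. Attribute a gain to training only so far as it exceeds that change.
3. State as a limitation that an abrupt change coinciding with training cannot be excluded.
4. Reconcile section 3.10.5 (three months, trained and untrained groups) with sections 3.7 and 3.9.3 for this service, which has no untrained group and for which six months of data are sought.
5. In the weight-service paragraph of section 3.9.3, reword the conclusion so that it refers to a difference between trained and untrained groups.

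The cost is a longer run of the same summary table, if the service holds data by quarter, and one further comparison. It needs no new consent or patient contact. The drawback is a less precise and probably less favourable estimate: on the assumptions above, the detectable effect rises from about 0.26 to 0.36 SD, or to 0.44 SD if the transitional quarter is left out.
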